### 8.3. Study Follow-Up Visits 1, 2, 3, 4, and 5 (Months 1, 6, 12, 18, and 24)

*This confidential document is the property of Abbott and shall not be reproduced, distributed, disclosed or used without the express written consent of Abbott*

## Clinical Investigation Plan

Implanted subjects will be evaluated at Month 1 ( $\pm$  7 days) and at Months 6, 12, 18, and 24 ( $\pm$  30 days) and the following procedures/assessments will be performed:

- Updated medical and surgical history
- Assessment of SAEs, ADEs, and SADEs that occurred since the last visit
- Reporting of any HF hospitalizations that have occurred since the last visit
- Abbreviated physical examination (significant changes since previous visit) including vital signs (heart rate, blood pressure), and weight
- Assessment of NYHA functional class
- Completion of Quality of Life Questionnaire EQ-5D-5L (6, 12, 18, and 24 month visits)
- Heart failure medication review
- PA pressure measurements may be obtained at the Investigator's discretion

Subjects will be reminded to obtain pulmonary artery pressure measurements utilizing the CardioMEMS HF System as directed. Subjects will be reminded of the current ACC/AHA guidelines or of the ESC guidelines regarding sodium and fluid restrictions.

### 8.4. Subject contact throughout the study

All contacts between site staff and study subjects post implant will be documented on a Subject Contact Log and the following information will be captured:

- Date of contact
- Reason for contact
- Ability to reach the subject (Call success)
- Name and role of person contacting the patient
- Call outcome (Instructions given)
- Other action required

### 8.5. Subject Home PA Pressure Readings

Following the sensor implant procedure, subjects will be instructed on how to take their own pulmonary artery pressure measurements, utilizing the CardioMEMS™ HF System. Subjects will provide returned demonstration on: setting up the unit, connecting the system to a phone line, proper positioning for obtaining the optimum sensor signal, taking and transmitting the daily pressure measurements. The unit will transmit the data to a database using the system's modem.

The home measurements will be taken while the subject is lying down (supine) in bed positioned on a padded, flat antenna. It is recommended that subjects obtain home measurements in a supine position however, if the subject is unable to lie flat, measurements can be obtained in a sitting or reclined position. It is important the anatomical position is consistent for every measurement.

*This confidential document is the property of Abbott and shall not be reproduced, distributed, disclosed or used without the express written consent of Abbott*

## Clinical Investigation Plan

The home electronics system is small enough for placement on a bedside table. The unit will provide audio and visual prompts for the subject to guide them through signal acquisition. Once the subject is positioned and a signal is acquired, the subject will be notified of the successful reading and the data is automatically transmitted to a remote database. St. Jude Medical will provide instructions for use and a help line will be available. Please refer to subject's Patient System Guide for more detailed information.

### 8.6. PA Pressure Readings in the hospital

If a subject is hospitalized, seen in the emergency room (ER) or has a clinic visit, the CardioMEMS™ HF System may be used to obtain pulmonary artery pressure measurements at the investigators discretion.

Following sensor implant, subsequent RHC procedures or pulmonary artery catheter insertions must be performed under fluoroscopic guidance.

Resetting of the sensor baseline will be performed as deemed necessary by Sponsor. Baseline resetting may require an echocardiogram or a RHC procedure.

Following the sensor implant, should a RHC procedure or PA catheter evaluation be clinically warranted, comparative pulmonary artery pressures utilizing the CardioMEMS™ HF System should also be obtained utilizing the hospital electronics unit.

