## Clinical Investigation Plan

Figure 1. CardioMEMS HF System

The system provides the physician with the patient's PA pressure waveform including systolic, diastolic, and mean pressures as well as heart rate. The Sensor is permanently implanted into the distal PA using transcatheter techniques in the catheterization laboratory; the sensor baseline is set to the mean PA pressure using a pulmonary artery catheter. Daily PA hemodynamic measurements are taken by the patient in a supine position at home. The patient measurement system consists of an antenna and electronics unit that guides the patient through the short reading process. The data can be recorded from the home, hospital, physician's office, or clinic. The hemodynamic data is transmitted to the website which is accessible via a secure website to the patient's physician or nurse.

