## Clinical Investigation Plan

### 8.2. Right Heart Catheterization and Implant Procedure (Baseline Visit)

Before the RHC, the following procedures/assessments will be performed:

- Abbreviated physical examination (i.e., vital sign assessments and significant changes since Screening Visit) and weight
- Confirmation of enrollment eligibility (other than angiographic criteria)
- PT/PTT with International Normalized Ratio (INR) per institution standards for subjects previously on warfarin
- Assessment of heart failure medications
- Record any changes in medical history that occurred since screening visit.

The patient will then undergo a standard RHC. A selective, hand injected pulmonary angiogram will be performed via the pulmonary artery catheter to identify a suitable pulmonary artery branch for sensor implantation. Subjects must have an appropriately sized ( $\geq 7\text{mm}$  diameter) pulmonary artery branch. These procedures are considered standard of care for the sensor implant and are described in the User Manual. Subjects who do not meet this inclusion criterion will not receive the PA Sensor implant and will be considered ineligible for the study. These subjects will be documented as consented not implanted and will be followed for 30 days for safety. Patients with a suitable target pulmonary artery branch will undergo:

- Wireless implantable hemodynamic sensor implant
- Pulmonary artery catheter measurements (pulmonary systolic, pulmonary diastolic, heart rate, pulmonary mean, cardiac output) done 3 times consecutively with sensor measurements for setting of sensor baseline.
- Provide post-procedure vascular access site care per standard procedure
- At the Investigator's discretion, subjects should be discharged once stable with respect to the procedure and their heart failure.
- Please see User's Manual for implant details

Subjects who are currently on anticoagulant therapy (warfarin or other approved anticoagulants) will restart treatment. The subject's INR should be checked per the institutions standards. Those subjects not on chronic warfarin will be placed on aspirin and clopidogrel or other approved anti-platelet daily for 1 month starting on the day of Sensor placement. Any approved anticoagulant or anti-platelet therapy may be used as well. After 1 month, the subject will continue with aspirin therapy and clopidogrel (or other approved anti-platelet therapy) will be discontinued.

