### 12.8.2.3. Patient Compliance

Patient device usage over the course of the trial will be examined. The total number of PA pressure readings taken will be reported as a percentage of patient days at home.

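### Compliance divides all PA pressure readings by days at home, so readings on inpatient days could inflate it

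*Combined protocol and SAP*

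**What the plan says.** Section 12.8.2.3 opens with the purpose, "Patient device usage over the course of the trial will be examined", and then gives the formula: "The total number of PA pressure readings taken will be reported as a percentage of patient days at home". The synopsis repeats that formula. Neither place restricts the count by location, operator or electronics unit, sets a limit per day, or says what makes a day a day at home.

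Readings outside the home are provided for in several places:

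- Section 3.4, on the system: "The data can be recorded from the home, hospital, physician's office, or clinic".
- Section 8.3, at the visits at Months 1, 6, 12, 18 and 24: "PA pressure measurements may be obtained at the Investigator's discretion". Section 8.7 makes a similar optional provision at study exit.
- Section 8.6: "If a subject is hospitalized, seen in the emergency room (ER) or has a clinic visit", the system "may be used to obtain pulmonary artery pressure measurements at the investigators discretion". When a later right heart catheterization or PA catheter evaluation is needed, comparative sensor readings "should also be obtained utilizing the hospital electronics unit".

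The synopsis and section 5 expect home readings daily, or as the investigator or physician directs.

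**The concern.** Numerator and denominator do not cover the same time. An inpatient day is not a day at home, but a reading made on it is still a reading taken. Each such reading raises the ratio, and the increment grows with inpatient days. A cap of one reading per day would not cure this, because the inpatient reading would still have no day to match. Separately, without a cap, a subject who reads twice on one day covers for a day with no reading.

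Home readings are how pressure data reach the investigator between visits, so the compliance figure helps readers interpret the effectiveness result. An increment that rises with hospitalization is tied to the primary outcome. It would blur any comparison of compliance between subjects or subgroups with different amounts of hospital time.

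**Working it through.** The plan gives no compliance figure, target or power statement, so there is nothing of its own to reproduce. The check sizes the gap between the literal formula and a home-only version.

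**Inputs from the documents**

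- HF hospitalization rate: 0.52 (Treatment) and 0.75 (Control) per patient-year, from CHAMPION as cited in section 12.2. The plan also uses 0.75 as its conservative planning rate.
- An HF hospitalization lasts at least 24 hours (Appendix F).
- Five scheduled follow-up visits over two years (section 8.3).

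**Assumptions, not in the documents**

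- Mean stay of 7 days, with a range of 5 to 14.
- One reading per inpatient day. Section 8.6 makes these readings optional, so this is an upper case for once-daily reading.
- HF stays only. The documents give no rate for other hospitalizations, whose inpatient days would add to the effect if read.

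**Formulas**

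- Literal = (home readings + facility readings) / home days
- Home-only = home readings / home days
- Excess = facility readings / home days, whatever the level of home compliance

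**Average over 365 days**, with inpatient days = rate × stay, home days = 365 − inpatient days, and excess in percentage points:

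| Stay (days) | 0.52 per year | 0.75 per year |
|---|---|---|
| 5 | 2.60 / 362.40 = 0.7 | 3.75 / 361.25 = 1.0 |
| 7 | 3.64 / 361.36 = 1.0 | 5.25 / 359.75 = 1.5 |
| 10 | 5.20 / 359.80 = 1.4 | 7.50 / 357.50 = 2.1 |
| 14 | 7.28 / 357.72 = 2.0 | 10.50 / 354.50 = 3.0 |

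With one reading per four inpatient days, each figure falls to a quarter. With none it is zero.

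**One heavily hospitalized subject**, with 40 inpatient days and 365 − 40 = 325 home days:

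- 163 home readings: home-only 163/325 = 50%. Literal, with daily inpatient readings, (163 + 40)/325 = 203/325 = 62%.
- 80% home compliance (260 home readings): literal 300/325 = 92.3% with daily inpatient readings, or 270/325 = 83.1% with one per four inpatient days.

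**Scheduled visits.** Five visit readings over 730 days contribute 5/730 = 0.7 point, or 5/725 = 0.7 point if visit days leave the denominator. The treatment of those days hardly matters for size. If a visit reading merely replaces that day's home reading and the day counts as a home day, actual use is not inflated.

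**Repeated readings.** Over ten home days, two readings on each of five days and none on the rest give 10/10 = 100%, although only half the days were covered.

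**The case against.** The strongest reply is that the plan never says facility readings are counted. The measure sits under a patient compliance heading and is introduced as patient device usage. Section 5 mentions compliance directly after home measurement, and the denominator is home days. Home readings over home days is a natural reading of the intent. This stands as far as it goes: it is not established that compliance will be overstated, only that the formula as written allows it. But the sentence that defines the calculation counts every reading, and nothing elsewhere narrows it. If home readings are meant, the text should say so.

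Other parts of the reply also stand:

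- A reader might infer that ER and clinic days drop out of the denominator. The plan does not say so. A day at home is undefined, and only inpatient days clearly fall outside it.
- A reader might add the sensor measurements at implant, "done 3 times consecutively with sensor measurements for setting of sensor baseline" (section 8.2). They precede discharge and serve calibration, so they are not plausibly patient compliance and are left out of the estimate.
- A reader might conclude that the sickest subjects will look the most compliant. That does not follow. The subject lifted from 50% to 62% still ranks below an unhospitalized subject at 80%. The increment is larger for those with more inpatient days, but it does not fix the ranking.
- Because readings may be directed less often than daily, dividing by all home days understates adherence for such subjects. The net error against each subject's own instruction is therefore not known. This is a separate limitation and does not repair the mismatch.

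**Conclusion.** The point holds as a mismatch in a stated formula. Inpatient readings, if taken and counted, enter the numerator without a matching day, and repeated readings can mask missed days. The first effect can only raise the figure relative to home-only compliance.

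On average it is small: about 1.0 to 1.5 points for 7-day stays read daily, and about 0.7 to 3.0 points across stays of 5 to 14 days at 0.52 to 0.75 HF hospitalizations per patient-year. For a single subject with 40 inpatient days read daily it reaches about 12 points (40/325). These sizes rest on assumed stay length and reading frequency, and the effect vanishes if staff take no inpatient readings.

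Compliance is a supplemental descriptive measure with no hypothesis or threshold. The primary safety and effectiveness conclusions are untouched, and this is a refinement rather than a serious fault.

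**What to change.** In the synopsis and section 12.8.2.3:

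1. Define compliance as the number of days at home after discharge with at least one reading taken by the patient at home, divided by the number of days at home after discharge. Counting days rather than readings also removes the offset from repeated readings.
2. Define a day at home, stating how admission and discharge days, ER attendances and clinic visits are treated.
3. Tabulate hospital, ER and clinic readings separately, and leave the implant baseline measurements out of compliance.

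The cost is a wording change and a filter on reading date and location. The synopsis already calls for information on all hospitalizations, which should supply the inpatient dates. A filter on electronics unit alone may not be enough: section 8.6 names the hospital unit only for comparisons at a catheter procedure and leaves the unit open for other facility readings. The sponsor should confirm that location can be derived for each reading. The reported compliance figure may come out slightly lower.

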### 8.7. Criteria for Withdrawal

Subjects may be withdrawn from the study for any of the following reasons:

1. Subject withdraws his/her consent
2. Investigator determines that other treatment is warranted to protect the health and safety of the subject
3. Investigator determines that the subject is noncompliant with study related procedures
4. Subject is lost to follow-up: site must document attempts made to contact the subject for an early discontinuation visit (e.g., 2 – 3 phone calls, followed by 1 certified letter, documentation of repetitive missed study visits, etc.)

The Investigator will notify the Sponsor and document on the appropriate CRF the reason/circumstances for early discontinuation. All subjects who withdraw from the study should have the following study exit procedures performed if possible:

- Assessment of SAEs, ADEs, and SADEs, that occurred since the last visit
- Reporting of any HF hospitalizations that have occurred since the last visit
- Abbreviated physical examination (only significant changes since Enrollment) including vital signs (temperature, heart rate, blood pressure), and weight
- Assessment of NYHA functional class
- Heart failure Medication Review
- PA pressures may be obtained at the Investigator's discretion

*This confidential document is the property of Abbott and shall not be reproduced, distributed, disclosed or used without the express written consent of Abbott*

## Clinical Investigation Plan

All reasonable efforts should be made to retain subjects in the clinical trial until its completion. If a patient moves from the geographic area of their investigator, St. Jude Medical will attempt to place the patient with another investigator.

### 8.8. Deviations from CIP

A deviation is defined as an instance(s) of failure to follow, intentionally or unintentionally, the requirements of the CIP. The investigator should not deviate from the CIP.

In some cases, failure to comply with the CIP may be considered failure to protect the rights, safety and well-being of subjects; such non-compliance exposes subjects to unreasonable risks. Examples: failure to adhere to the inclusion/exclusion criteria, failure to report SAEs within given timeframe as per CIP, etc. Investigators should seek to minimize such risks by adhering to the CIP.

The PI must maintain accurate, complete, and current records, including documents showing the date of and reason for each deviation from the CIP. Relevant information for each deviation will be documented as soon as possible on the applicable CRF. The site will submit the CRF to the Sponsor.

The PI is required to adhere to local regulatory requirements for reporting deviations to the site IEC.

## Clinical Investigation Plan

### 9. SAFETY ANALYSES

#### 9.1. Primary Safety Endpoints

Primary safety endpoints will be evaluated at 2 years:

- 1) Freedom from device/system related complications
- 2) Freedom from pressure sensor failure

##### 9.1.1. Device / System-related Complication Criteria

A device / system-related complication is an adverse event that is, or is possibly, related to the system (wireless pressure sensor or external electronics) and has at least one of the following characteristics:

- is treated with invasive means (other than intramuscular medication or a right heart catheterization which is used for diagnostic purposes)
- results in the death of the subject
- results in the explant of the device

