#### 3.4. CardioMEMS™ HF System

The CardioMEMS™ HF System provides pulmonary artery (PA) hemodynamic data used for the monitoring and management of heart failure (HF) patients. The system measures changes in PA pressure which physicians use to initiate or modify heart failure treatment.

[figure not shown]
The system includes the following components:

- Implantable wireless sensor with delivery catheter
- Patient or hospital electronics system
- Patient database (Merlin.net Website)

*This confidential document is the property of Abbott and shall not be reproduced, distributed, disclosed or used without the express written consent of Abbott*

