## Clinical Investigation Plan

### **11. ADVERSE EVENTS**

#### **11.1. Adverse Event (AE)**

An adverse event (AE) is any untoward medical occurrence, unintended disease or injury, or untoward clinical signs (including abnormal laboratory findings) in subjects, users or other persons, whether or not related to the medical device under investigation.

Note 1: This definition includes events related to the medical device under investigation or the comparator.

Note 2: This definition includes events related to the procedures involved.

Note 3: For users or other persons, this definition is restricted to events related to medical devices under investigation.

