#### **11.3. Device-Relatedness**

An AE or SAE that is definitely or possibly related to the device or the insertion procedure should be considered device-related. A serious adverse device effect (SADE) is an event that meets any of the above SAE criteria and is considered definitely or possibly related to the device or the insertion procedure by the Investigator. All other events considered definitely or possibly related to the device or insertion procedure are non-serious adverse device effects (ADEs).

If it is not certain that an event meets the above definitions, contact the Study Manager.

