#### **12.1. Populations for Analysis**

**Safety Population:** The Safety Population consists of all subjects who received a Sensor implant or underwent the implant procedure but were never implanted, regardless of study completion status. All safety analyses will be performed on the Safety population.

Subjects who are found not to have an appropriately sized pulmonary artery branch and did not receive the Sensor implant will be considered ineligible for the study. However, these subjects will be followed for 30 days for safety and all safety related data for these subjects will be provided.

**Effectiveness Population:** The effectiveness population consists of all subjects who received a Sensor implant regardless of study completion status. All effectiveness analyses will be performed on the effectiveness population.

**Pooled Safety Population:** The Pooled Safety Population will consist of the Safety Population from this study and the Safety Population from other similar study(ies) (demonstrated to be poolable with this study) that have been combined to form a larger safety analysis population to permit more robust analyses.

**Pooled Effectiveness Population:** The Pooled Effectiveness Population will consist of the Effectiveness Population from this study and the Effectiveness Population from other similar study(ies) (demonstrated to be poolable with this study) that have been combined to form a larger effectiveness analysis population to permit more robust analyses.

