### 12.3. Safety Sample Size Determinations

The freedom from device-related complications observed in CHAMPION over 2 years was 98.6%. For the two-year primary safety endpoint of freedom from device-related complications, using an exact one-sided test for one-sample binomial proportions with alpha of 0.025 (equivalent to 2-sided test at alpha of 0.05) (see table below), a sample size of 137 subjects will provide greater than 90% power to detect a difference as small as 10% from the null proportion rate of 0.80 (i.e., objective performance criterion of 80%). For sensor failures at 2 years, a sample size of 292 subjects provides greater than 90% power to detect a difference as small as 5.0% from the null proportion rate of 0.90 (i.e., objective performance criterion of 90%)(see table below).

To account for early withdrawal, and to allow additional countries to enroll sufficient number of subjects each, 800 subjects will be enrolled.

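### The primary complication endpoint covers only the sensor and external electronics, so delivery-catheter and insertion complications that sections 3.4 and 11.3 would attribute to the device can drop out of the reported rate

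*Combined protocol and SAP*

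**What the plan says.** Section 9.1.1 sets two conditions for a device/system-related complication. The event must be, or possibly be, "related to the system (wireless pressure sensor or external electronics", and it must need invasive treatment, kill the subject, or lead to removal of the device. Section 12.7.1 tests freedom from these complications at 24 months against 80% and does not redefine the term.

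Three other places draw the boundary more widely:

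- Section 3.4 names as one system component the "Implantable wireless sensor with delivery catheter".
- Section 11.3 says that an event "definitely or possibly related to the device or the insertion procedure should be considered device-related". It classes such events as SADEs if they meet the serious criteria and as ADEs otherwise.
- Section 11.1, in a note to the adverse event definition, says: "This definition includes events related to the procedures involved".

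The Safety Population in section 12.1 also takes in subjects who "underwent the implant procedure but were never implanted, regardless of study completion status".

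**The concern.** The primary safety endpoint and the ADE/SADE tables appear to use different meanings of device-related, and the endpoint has the narrower one. If a delivery-catheter or insertion injury needs invasive treatment or is fatal, but the sensor is not suspected, it meets 9.1.1 on seriousness and fails it on relatedness. The reported rate would then describe the sensor and electronics, while the stated objective is to confirm safety of the system in real-world use.

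The mismatch is sharpest for subjects who had the procedure but no implant. They are in the Safety Population, yet under the bracket in 9.1.1 they can rarely have an endpoint event.

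Consistency is also at stake. Relatedness for SADEs is the investigator's judgement, up to 85 sites take part, the revision history says there is no Clinical Events Committee, and the current text names no other adjudicator. Some sites may follow the bracket and others section 11.3.

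**Working it through.** **Step 1: the definitions side by side.** Take a vessel injury made during insertion, treated invasively, with no possible sensor involvement.

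| Section | Test applied | Result |
|---|---|---|
| 11.3 | Related to device or insertion procedure | ADE, or SADE if serious |
| 3.4 | Is the delivery catheter part of the system? | Yes |
| 9.1.1, seriousness | Invasive treatment | Met |
| 9.1.1, relatedness | Sensor or external electronics | Not met on the literal wording |

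**Step 2: reproduce the plan's own figure.** Section 12.3 uses an exact one-sided binomial test, with target alpha 0.025 and a "null proportion rate of 0.80 (i.e., objective performance criterion of 80" per cent. With n = 137 and rejection at 119 or more event-free subjects:

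- alpha = P(X ≥ 119 | n = 137, p = 0.80) = 0.0245
- power = P(X ≥ 119 | n = 137, p = 0.90) = 0.9100

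Both match the table, as do its other eight rows. The definition does not affect this arithmetic. It decides which events enter the proportion.

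**Step 3: the threshold at 800.** The smallest r with P(X ≥ r | n = 800, p = 0.80) ≤ 0.025 is 663 (alpha 0.0218; 662 gives 0.0271). So 663/800 = 82.9% passes, which allows 800 − 663 = 137 subjects with an event.

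**Step 4: sensitivity.** Section 12.3 states: "The freedom from device-related complications observed in CHAMPION over 2 years was 98.6" per cent. Let x be the share of subjects whose only complication is catheter- or procedure-related. The documents give no value, so x is an assumption. Three further assumptions are that 98.6% is the rate on the narrow definition, that x adds to it, and that all 800 subjects are evaluable.

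- True freedom on the broader definition = 0.986 − x
- Expected events = 800 × (0.014 + x)
- Power = P(X ≥ 663 | n = 800, p = 0.986 − x), and likewise with 119 and n = 137

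| x | Freedom | Expected events, n = 800 | Power, n = 800 | Power, n = 137 |
|---|---|---|---|---|
| 0 | 98.6% | 11.2 | 1.00 | 1.00 |
| 1% | 97.6% | 19.2 | 1.00 | 1.00 |
| 2% | 96.6% | 27.2 | 1.00 | 1.00 |
| 3% | 95.6% | 35.2 | 1.00 | 1.00 |
| 5% | 93.6% | 51.2 | 1.00 | 0.999 |
| 10% | 88.6% | 91.2 | 1.00 | 0.78 |
| 15% | 83.6% | 131.2 | 0.73 | 0.18 |

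Each 1% moves the rate by one point, or 0.01 × 800 = 8 subjects. The count is more sensitive than the test: x = 1% takes expected events from 11.2 to 19.2.

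**The case against.** The strongest reply is that the wording is ambiguous rather than exclusive. Section 9.1.1 includes possibly related events. The sensor and catheter are listed together in 3.4, so the bracket may be shorthand for both. The endpoint is labelled device/system-related, and a reader could bring in 11.3 through the word device. This stands as far as it goes: such events can escape the endpoint, but need not. It does not remove the problem, because the plan never says which reading applies.

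Second, the events are still reported. Section 11.5 collects ADEs, SAEs and SADEs, Appendix A has an adverse event assessment at the implant visit, and section 12.7.1 tabulates events by relationship to the device. That stands: the loss is from the primary rate, not from safety reporting.

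Third, the 80% criterion comes from CHAMPION, and widening the endpoint could break the match with it. That stands too. The documents do not give CHAMPION's complication definition, so it cannot be said which wording preserves the match. This argues against simply replacing the primary definition.

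Some stronger readings are tempting but unsupported:

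- A reader might infer that the endpoint omits the main source of harm. Section 11.7 names the implant procedure as a risk source but leaves incidence to the User's Manual.
- A reader might take some share of the 11 expected events as the number omitted. If 98.6% already rests on a narrow definition, the omitted events come on top of the 11. If it rests on a broad one, they lie within it. The documents do not settle this.
- A reader might infer that never-implanted subjects are scored as event-free at 24 months. The 24-month time point runs from enrolment, which requires a successful implant, and those without a suitable artery are followed for 30 days. No section says how they enter the 24-month proportion.

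**Conclusion.** The inconsistency between 9.1.1 on one side and 3.4 and 11.3 on the other is real, and it lies in a primary endpoint. On the literal wording, a complication of delivery or insertion without possible sensor involvement does not count in the primary rate.

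The size is one percentage point of reported freedom for each 1% of subjects affected, with that percentage unknown. The inference that the trial could wrongly pass its safety test is not supported. With 800 evaluable subjects and 98.6% as the starting point, power against 80% is about 1.00 up to 10 points of extra events and 0.73 at 15. The margin is thinner at the minimum sample of 137 (0.78 at 10 points), but enrolment is planned well above that. What is affected is the estimate and what it can be said to show about the safety of the whole system.

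**What to change.** Reconcile 9.1.1 with 3.4 and 11.3 by pre-specifying a second 24-month freedom-from-complication rate. Keep the same three seriousness criteria, and count events definitely or possibly related to the sensor, the delivery catheter, the external electronics or the insertion procedure. State whether insertion procedure includes the right heart catheterization and the angiogram, since some subjects have these without any use of the delivery system.

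Report this rate beside the sensor-and-electronics rate. State which of the two is tested against 80%, after checking which definition the CHAMPION criterion used. Say also how never-implanted subjects enter each rate.

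The cost is one added analysis on data that the study already collects, a protocol amendment with the ethics committee and regulatory steps in section 14.2, and a broader rate that may look slightly less favourable.
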